3.4.1.1 Multiple Imputation

Step 1 (imputing missing data): Thirty multiple imputed complete datasets were to be constructed using imputation regression model of baseline sSOL, baseline ISI, age, sex, race (white, black, and other), and region (North America, Europe and New Zealand, Asia), baseline BMI, baseline log(sSOL), baseline ISI with a predefined arbitrary seed number (seed=2006). SAS PROC MI will be used to implement the imputation procedure using all available values. The dataset will be converted into monotone missing pattern by imputing arbitrary missing data as the first step. The monotone data will then be imputed with monotone regression method and MNAR. The sample SAS statement can be found in [Section 7](#).

Step 2 (performing MMRM using each imputed dataset): The MMRM model with factors of age group (<65 years old, ≥65 years old), region (North America, Europe and New Zealand, Asia), treatment, visit (1st 7 nights, Month 1, Month 2, Month 3, Month 4, month 5 and Month 6), and treatment-by-visit interaction as fixed effect, and the baseline log(sSOL) as a covariate will be applied to each imputed dataset. SAS PROC MIXED will be used for the MMRM analysis. The sample SAS statement can be found in [Section 7](#).

Step 3 (combine results): Resulting treatment effect parameter estimators and standard errors from each of 30 multiple imputed datasets from Step 2 will be combined using SAS PROC MIANALYZE to obtain the pooled treatment effect and variance parameter estimators according to Rubin's rules ([Rubin DB, 1987](#)). The sample SAS statement can be found in [Section 7](#).

3.4.1.2 Subgroup Analyses

The primary endpoints described in [Section 3.4.1](#) will be summarized using descriptive statistics by each subgroup listed below. No hypothesis testing will be performed in the subgroup analyses.

- Age group 1 (< 65, 65 to < 75, ≥75 years old)
- Age group 2 (<65, ≥65 years old)
- Sex (male and female)
- Race (white, black, Asian and other)
- Region (North America, Europe and New Zealand, Asia)
- BMI group (kg/m²) (<18.5, 18.5 to <25, ≥25 to 30, >30 kg/m²)

3.4.1.3 Sensitivity Analyses

The following analyses will be considered as sensitivity analyses:

- MI Imputation assuming MNAR utilizing CCMV-7: The same MMRM method used in the primary analysis will be applied utilizing CCMV-7 (ie, up to 7 monotone missing patterns will be used for missing value imputation as follows):

Table 5 Monotone Missing Patterns for Primary Efficacy Analysis

Timepoints where results are available	Wk1	M1	M2	M3	M4	M5	M6
Pattern 1	x	x	x	x	x	x	x
Pattern 2	x	x	x	x	x	x	.
Pattern 3	x	x	x	x	x	.	.
Pattern 4	x	x	x	x	.	.	.
Pattern 5	x	x	x
Pattern 6	x	x
Pattern 7	x

Wk1=week1; M1=month1; M2=month2; M3=month3; M4=month4; M5=month5; M6=month6;
x=observed data; .=missing data

- Tipping point analysis: A range of shifts starting from the primary analysis (CCMV) will be used in the multiple imputation of missing data assuming MNAR to identify the specific shift and treatment effect that will tip the results from statistically significant to non-significant.
- The same primary efficacy analyses described in [Section 3.4.1](#) (MMRM analysis with MI for missing value imputation) will be repeated based on non-Log transformed data.
- A MI Imputation assuming MNAR utilizing CCMV-7: The same MMRM method used in the primary analysis will be applied utilizing CCMV-7 based on non-Log transformed data.
- Tipping point analysis based on non-Log transformed data: A range of shifts starting from the primary analysis (CCMV) will be used in the multiple imputation of missing data assuming MNAR to identify the specific shift and treatment effect that will tip the results from statistically significant to non-significant.

3.4.1.4 Supplementary Analyses

The following analyses will be considered as supplementary analyses:

- PP analysis: The same primary efficacy analyses described in [Section 3.4.1](#) (MMRM analysis with MI for missing value imputation) will be repeated based on PP analysis set.
- Completer analysis: The same primary efficacy analyses described in [Section 3.4.1](#) (MMRM analysis without missing value imputation) will be repeated on 6-Months Completer Analysis Set.

- MMRM analysis assuming MAR: The same primary endpoint analysis described above will be analyzed using MMRM assuming the missing values are missing at random (MAR; MMRM analysis without missing value imputation).
- MMRM analysis assuming MAR: The same primary endpoint analysis described above will be analyzed using MMRM assuming the missing values are missing at random (MAR; MMRM analysis without missing value imputation) based on non-Log transformed data.

3.4.2 Secondary Efficacy Analyses

3.4.2.1 Key Secondary Efficacy Analyses

The change from Study Baseline of key secondary endpoints sSE and sWASO at Month 6 comparing LEM10/LEM5 to PBO will be analyzed as follows.

CHANGE FROM STUDY BASELINE OF SSE AT MONTH 6

The change from Study Baseline of sSE at Month 6 will be analyzed using the mixed effect model repeated measurement (MMRM) analysis on the FAS. The model will be adjusted for the corresponding Study Baseline value, region (North America, Europe and New Zealand, Asia), age group (<65 years old, ≥65 years old), treatment, time (1st 7 nights, Month 1, Month 2, Month 3, Month 4, Month 5 and Month 6) and the interaction of treatment by time. The unstructured covariance matrix (UN) will be used in the analysis. In the case of non-convergence of UN, the toeplitz covariance matrix (TOEP) will be used. In the case of non-convergence with TOEP, the autoregressive covariance matrix [AR(1)] will be used in the model.

Before the implementation of the MMRM model, the missing values will be imputed using a pattern mixture model utilizing multiple imputation (MI) assuming the missing values are missing not at random (MNAR). The missing values for a given visit will be imputed using all available values including the retrieved measurement from the post-discontinuation data.

The treatment comparison will be performed using contrasts. The p-value, least square (LS) means and the 95% confidence interval (CI) for the treatment difference will also be provided.

MULTIPLE IMPUTATION

The same 3 steps (imputing missing data, performing MMRM using each imputed dataset, and combine results) will be implemented as described in [Section 3.4.1](#). The complete data sets will be constructed using regression model of age, sex, race (white, black, and other), region (North America, Europe and New Zealand, Asia), baseline BMI, baseline mean sSE, baseline ISI, and mean sSE at first 7 nights, mean sSE at Month 1, mean sSE at Month 2, mean sSE at Month 3, mean sSE at Month 4, mean sSE at Month 5 and mean sSE at Month 6. 50 multiple imputed datasets will be used for sSE, where data are truncated to 0 (where imputations <0) and 100 (where imputations >100).

CHANGE FROM STUDY BASELINE OF sWASO ON MONTH 6

The change from Study Baseline of sWASO on Month 6 will be analyzed using the mixed effect model repeated measurement (MMRM) analysis on the FAS. The model will be adjusted for the corresponding Study Baseline value, region (North America, Europe and New Zealand, Asia), age group (<65 years old, ≥65 years old), treatment, time (1st 7 nights, Month 1, Month 2, Month 3, Month 4, Month 5 and Month 6) and the interaction of treatment by time. The unstructured covariance matrix (UN) will be used in the analysis. In the case of non-convergence of UN, the toeplitz covariance matrix (TOEP) will be used. In the case of non-convergence with TOEP, the autoregressive covariance matrix [AR(1)] will be used in the model.

Before the implementation of the MMRM model, the missing values will be imputed using a pattern mixture model utilizing multiple imputation (MI) assuming the missing values are missing not at random (MNAR). The missing values for a given visit will be imputed using all available values including the retrieved measurement from the post-discontinuation data.

The treatment comparison will be performed using contrasts. The p-value, least square (LS) means and the 95% confidence interval (CI) for the treatment difference will also be provided.

MULTIPLE IMPUTATION

The same 3 steps (imputing missing data, performing MMRM using each imputed dataset, and combine results) will be implemented as described in [Section 3.4.1](#). The complete data sets will be constructed using regression model of age, sex, race (white, black, and other), region (North America, Europe and New Zealand, Asia), baseline BMI, baseline mean sWASO, baseline ISI, and mean sWASO at first 7 nights, mean sWASO at Month 1, mean sWASO at Month 2, mean sWASO at Month 3, mean sWASO at Month 4, mean sWASO at Month 5 and mean sWASO at Month 6.

3.4.2.2 Sensitivity Analyses for Key Secondary Efficacy Analyses

The following analyses will be considered as sensitivity analyses:

- MI Imputation utilizing CCMV-7: The same MMRM method used in the primary analysis will be applied utilizing CCMV-7 (ie, up to 7 monotone missing patterns will be used for missing value imputation as follows):

Table 6 Monotone Missing Patterns for Secondary Efficacy Analysis

Timepoints where results are available	Wk1	M1	M2	M3	M4	M5	M6
Pattern 1	x	x	x	x	x	x	x
Pattern 2	x	x	x	x	x	x	.
Pattern 3	x	x	x	x	x	.	.
Pattern 4	x	x	x	x	.	.	.
Pattern 5	x	x	x
Pattern 6	x	x
Pattern 7	x

Wk1=week1; M1=month1; M2=month2; M3=month3; M4=month4; M5=month5; M6=month6;
x=observed data; .=missing data

- Tipping point analysis: A range of shifts starting from the primary analysis (CCMV) will be used in the multiple imputation of missing data to identify the specific shift and treatment effect that will tip the results from statistically significant to non-significant.

3.4.2.3 Supplementary Analyses for Key Secondary Efficacy Analyses

The following analyses will be considered as supplementary analyses:

- PP analysis: The same primary efficacy analyses described in [Section 3.4.1](#) (MMRM analysis with MI for missing value imputation) will be repeated based on PP analysis set.
- Completer analysis: The same primary efficacy analyses described in [Section 3.4.1](#) (MMRM analysis without missing value imputation) will be repeated on 6-Months Completer Analysis Set.
- MMRM analysis assuming MAR: The same primary endpoint analysis described above will be analyzed using MMRM assuming the missing values are missing at random (MAR; MMRM analysis without missing value imputation).

3.4.2.4 Other Secondary Efficacy Analyses

For all other secondary endpoints described below, the continuous variable will be summarized by using descriptive statistics by time point and the categorical variable will be summarized as the number and percentage of subjects by time point.

Unless is covered from the same model from the primary and secondary efficacy endpoints, or specified otherwise, the change from baseline assessments will be analyzed using MMRM assuming MAR (no missing value imputation) and the portion of responders will be analyzed using the Cochran Mantel Haenszel (CMH) test adjusted for region and age group. Missing values will be considered as non-responders in all responder analyses. No multiplicity adjustment will be made for all analyses.

The following endpoints will be analyzed.

EFFICACY MEASURES DERIVED FROM THE SLEEP DIARY

- Change from Study Baseline of mean sSOL, mean sSE, mean sWASO and mean sTST for the 1st 7 nights, Months 1, 2, 3, 4 and 5; and mean sTST at Month 6; for LEM5 and LEM10 compared to PBO
- Change from Study Baseline/ Treatment Period 2 Baseline of mean sSOL, mean sSE, mean sWASO and mean sTST for 1, 3, 6, 9 and 12 months exposure to LEM5 and LEM10. . Data from subjects randomized to LEM5 or LEM10 at the start of the study will use Study Baseline, data from subjects who were re-randomized to LEM5 or LEM10 in Period 2 will use Treatment Period 2 Baseline.
- The proportion of responders, separately for sSOL and sWASO, will be analyzed, for the first 7 nights, Months 1, 2, 3, 4, 5 and 6 for LEM5 and LEM10 compared to PBO:
 - The sleep onset responder is defined as: sSOL at Study Baseline is >30 minutes and mean sSOL at each month (first 7 nights, Months 1, 2, 3, 4, 5, 6) is ≤ 20 minutes,
 - The sleep maintenance responder is defined as: sWASO at Study Baseline is >60 minutes and mean sWASO at each month (first 7 nights, Months 1, 2, 3, 4, 5, 6) is ≤ 60 minutes and shows a reduction of >10 minutes compared to Study Baseline.

The proportion of responders will be analyzed based on the subjects with sSOL > 30 minutes at the baseline for sSOL and separately the subjects with sWASO > 60 minutes at the baseline for sWASO.

- The proportion of responders, separately for sSOL and sWASO, at Months 7, 8, 9, 10, 11 and 12 will also be summarized by using two types of baseline (ie., Study Baseline, Period 2 Baseline). The definition of the responder at Month 7, 8, 9, 10, 11 and 12 will be as follows:
 - The sleep onset responder is defined as: sSOL at Study Baseline (or Period 2 Baseline) is >30 minutes and mean sSOL at each month (Months 7, 8, 9, 10, 11 and 12) is ≤ 20 minutes,
 - The sleep maintenance responder is defined as: sWASO at Study Baseline (or Period 2 Baseline) is >60 minutes and mean sWASO at each month (Months 7, 8, 9, 10, 11

and 12) is ≤ 60 minutes and shows a reduction of >10 minutes compared to Study Baseline (or Period 2 Baseline).

The proportion of responders will be analyzed based on the subjects with sSOL > 30 minutes at the baseline for sSOL and separately the subjects with sWASO > 60 minutes at the baseline for sWASO.

- Morning sleepiness item of the Sleep Diary:
 - Change from Study Baseline of mean rating on morning sleepiness at the 1st 7 mornings after the 1st dose in Treatment Period 1, Month 1, Month 2, Month 3, Month 4, Month 5 and Month 6.
 - Change of mean rating on morning sleepiness from Study Baseline / Treatment Period 2 Baseline for 1st 7 mornings after the 1st LEM dose, 1, 3, 6, 9 and 12 months of exposure to LEM5 and LEM10. Data from subjects randomized to LEM5 or LEM10 at the start of the study will use Study Baseline, data from subjects who were re-randomized to LEM5 or LEM10 in Period 2 will use Treatment Period 2 Baseline. Change from Screening of mean rating on morning sleepiness of 1st 7 mornings and 2nd 7 mornings in Follow-Up Period.
- Rebound insomnia endpoints during the Follow-up Period as follows:
 - Change from Screening of sSOL on each of the 1st 3 nights, mean sSOL of the 1st 3 nights, mean sSOL of the 1st 7 nights, and mean sSOL of the 2nd 7 nights of the Follow-up Period
 - Change from Screening of sWASO on each of the 1st 3 nights, mean sWASO of the 1st 3 nights, mean sWASO of the 1st 7 nights and mean sWASO of the 2nd 7 nights of the Follow-up Period
 - Proportion of subjects whose sSOL is longer than at Screening by at least 5 minutes for each of the 1st 3 nights, mean sSOL of the 1st 3 nights, mean of the 1st 7 nights, and mean of the 2nd 7 nights of the Follow-up Period
 - Proportion of subjects whose sWASO is higher than at Screening by at least 5 minutes for each of the 1st 3 nights, mean sWASO of the 1st 3 nights, mean of the 1st 7 nights, and mean of the 2nd 7 nights of the Follow-up Period.

The actual value of sSOL and sWASO will be analyzed separately using analysis of covariance model (ANCOVA) with factors of age group (<65 , and ≥ 65 years older), region (North America, Europe and New Zealand, Asia), and treatment for each time point (baseline, each of the first 3 nights, mean of the first 3 nights, mean of the first 7 nights, and mean of the last 7 nights of the Follow-up Period). The 95% CI of the treatment difference will be constructed for each time point. It will be considered as strong evidence of rebound insomnia if the lower bound of the 95% CI of sSOL or sWASO for each of the 3 nights, the mean of the first 3 nights, mean of the first 7 nights, and mean of the second 7 nights of the Follow-up Period exceeds the upper bound of a 95% CI for the values during the Screening Period in the given treatment group. If the LS means for sSOL and sWASO for the Follow-up Period are all lower than for the Screening Period, then no rebound insomnia is suggested. In this analysis, the treatment groups will be defined as the last randomized study treatment just before the Follow-up period.

- Analyses for persistence versus loss of effect will be conducted for sSOL, sSE, sWASO and sTST at Months 2 through Month 12 compared to Month 1.

The 95% CI for the change from Study Baseline of sSOL, sSE, sWASO and sTST at each visit will be calculated using the MMRM model assuming MAR (no missing value imputation) with factors of age group (<65, and ≥65 years older), region (North America, Europe and New Zealand, Asia), treatment, visit and treatment-by-visit interaction as fixed effect, and baseline value as covariate based on FAS. At each month beyond Month 1, the change from Study Baseline will be compared to either the lower bound of the 95% CI (for sSE and sTST) or the upper bound of the 95% CI (for sSOL and sWASO) at Month 1. Persistence of effect will be defined as present if the mean change from Study Baseline at Month 6 is above the lower bound of the 95% CI at Month 1 for sSE or sTST and below the upper bound of the 95% CI at Month 1 for sSOL and sWASO.

The same analyses for persistence versus loss of effect over Period 2 will compare sSOL, sSE, sWASO, and sTST at Months 7 through 12 to these measures at Month 7 for only the subjects who were randomized to PBO in Period 1 and who continued into Period 2. At each month beyond Month 7, the change from Treatment Period 2 Baseline will be compared to either the lower bound of the 95% CI (for sSE and sTST) or the upper bound of the 95% CI (for sSOL and sWASO) at Month 7. Persistence of effect will be defined as present if the mean change from Treatment Period 2 Baseline at Month 12 is above the lower bound of the 95% CI at Month 7 for sSE or sTST and below the upper bound of the 95% CI at Month 7 for sSOL and sWASO.

Analyses for persistence versus loss of effect over duration of exposure will be conducted for On-Treatment Full Analysis Set subjects. These analyses will compare 1 month of duration of exposure of sSOL, sSE, sWASO and sTST at 3 and 6 months duration of exposure, for a) LEM Period 1 subjects using the change from Study Baseline and (b) LEM Period 2 subjects previously receiving PBO using the change from Period 2 Baseline. At 3 and 6 months duration of exposure, the change from Study Baseline/Treatment Period 2 Baseline will be compared to either the lower bound of the 95% CI (for sSE and sTST) or the upper bound of the 95% CI (for sSOL and sWASO) at 1 month duration of exposure. Persistence of effect will be defined as present if the mean change from Study Baseline/Treatment Period 2 Baseline at 6 months of exposure is above the lower bound of the 95% CI at 1 month of exposure for sSE or sTST and below the upper bound of the 95% CI at 1 month of exposure for sSOL and sWASO.

INSOMNIA SEVERITY INDEX AND FATIGUE SEVERITY SCALE

The following endpoints will be analyzed for the ISI and FSS:

- Change from Study Baseline of the total score from items 1-7, and items 4-7, separately, on the ISI at Months 1, 3, 6 of LEM5 and LEM10 compared to PBO.

- Change from Study Baseline and Treatment Period 2 Baseline (as appropriate) of the total score from items 1-7, and items 4-7, separately, on the ISI for subjects with 3, 6, 9 and 12 months of exposure.
- Change from Study Baseline on the FSS score at Months 1, 3, 6 of LEM5 and LEM10 compared to PBO
- Change from Study Baseline and Treatment Period 2 Baseline (as appropriate) on the FSS score for subjects with 3, 6, 9 and 12 months of exposure.

The FSS will be further analyzed to evaluate whether lemborexant treatment affected fatigue severity in those who entered the study with clinically significant levels of fatigue. These subgroup analyses will include only those whose total FSS score was ≥ 18 at Study Baseline, which can be considered the lower threshold on the FSS for the presence of clinically significant fatigue. Analyses using the FSS analysis model will then be applied. In addition, S-plot figures will show the proportion of subjects with varying rates of response on the FSS as follows:

- Cumulative proportion of subjects with varying absolute decreases from Study Baseline in total FSS score: the x-axis will show decrease from baseline in 5-unit increments up to a ≥ 40 -unit decrease from baseline at Months 1, 3 and 6. Responder rates of -10 and -30 units will be marked on the S-Plot.
- Cumulative proportion of subjects with varying relative decreases from Study Baseline in total FSS score: the x-axis will show decrease from baseline in 10% increments up to a 100% decrease from baseline at Months 1, 3 and 6. Responder rates of -10% and -30% will be marked on the S-Plot.

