	-11	241	723	323	969
	-11.4	225	675	300	900
	-12	203	609	271	813

CfB = change from baseline, sSOL = subjective sleep onset latency, sWASO = subjective wake after sleep onset.

The study also had adequate power for the secondary analysis of responders. A sleep onset responder was defined as follows: sSOL at Study Baseline was ≥ 30 minutes and mean sSOL at 6 months was ≤ 20 minutes, and a sleep maintenance responder was defined as follows: sWASO at Study Baseline was ≥ 60 minutes and mean sWASO at 6 months was ≤ 60 minutes and showed a reduction of > 10 minutes compared to Study Baseline. A total of 900 subjects gave >99% power to detect a treatment difference in sleep onset responder rates of 16% and sleep maintenance responder rates of 24.4%, both compared with placebo.

The above sample size also met regulatory safety requirements. Even with early discontinuation rates as high as 50% at Month 6 (ie, 150 subjects remaining) and 60% by Month 12 (ie, 120 subjects remaining in each treatment group), the requirement for 100 subjects in each of the elderly and non-elderly age-groups to complete 12-months of treatment on 5 or 10 mg lemborexant would be met. In addition, a total of 420 subjects would complete 6 months of treatment with 5 or 10 mg lemborexant.

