3.1.2 Secondary Endpoints

The key secondary endpoints are:

- Mean change from Study Baseline in sSE at Month 6

- Mean change from Study Baseline of sWASO at Month 6

Additional secondary endpoints are:

- Mean change from Study Baseline of sSOL, of sSE, of sWASO and of sTST, at the beginning of treatment (mean of the 7 nights after the 1st dose in Period 1), at Month 1 and at Month 3
- Mean change from Study Baseline of sTST at Month 6
- Proportion of responders at Month 6 and Month 12, where sleep onset responder is defined as follows: sSOL at Study Baseline is ≥ 30 minutes and mean sSOL at 6 months is ≤ 20 minutes, and sleep maintenance responder is defined as follows: sWASO at Study Baseline is ≥ 60 minutes and mean sWASO at 6 months is ≤ 60 minutes and shows a reduction of >10 minutes compared to Study Baseline.
- Change from Study Baseline in daytime functioning, assessed as the total score from the 4 items on daytime functioning, on the ISI, at Months 1, 3, and 6
- Change from Study Baseline on the FSS at Months 1, 3, and 6
- Ratings on the morning sleepiness item of the Sleep Diary, for:
 - The mean change from Study Baseline of the 1st 7 mornings after the 1st dose in Period 1 and Period 2
 - The mean change from Study Baseline at: Month 1, Month 3, and Month 6
 - The mean change from Study Baseline and from Treatment Period 2 Baseline (as appropriate): for subjects with 1, 3, 6, 9 and 12 months exposure
 - The mean change from Screening for the 1st 7 mornings and 2nd 7 mornings of the Follow-up Period
- Rebound insomnia endpoints as assessed from the Sleep Diary during the Follow-up Period
 - Change from Screening of sSOL on each of the 1st 3 nights, mean sSOL of the 1st 7 nights, and mean sSOL of the 2nd 7 nights of the Follow-up Period
 - Change from Screening of sWASO on each of the 1st 3 nights, mean sWASO of the 1st 7 nights and mean sWASO of the 2nd 7 nights of the Follow-up Period
 - Proportion of subjects whose sSOL is longer than at Screening for each of the 1st 3 nights, or whose mean sSOL is longer than at Screening for 1st 7 nights or 2nd 7 nights of the Follow-up Period
 - Proportion of subjects whose sWASO is higher than at Screening for each of the 1st 3 nights, or whose mean sWASO is higher than at Study Baseline for the 1st 7 nights or 2nd 7 nights of the Follow-up Period
- Persistence of Effect
 - Mean change from Study Baseline of sSOL, of sSE, of sWASO and of sTST at Months 3, 6, 9, and 12 compared to Month 1

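### SAP 3.4.2.4 uses strict baseline cuts (>30 and >60 minutes) for the responder analyses, where the protocol endpoint and SAP 2 and 3.1.2 use ≥30 and ≥60

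*SAP*

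**What the plan says.** Inclusive cuts:

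- SAP 3.1.2, sleep onset: "sSOL at Study Baseline is ≥ 30 minutes and mean sSOL at 6 months is ≤ 20 minutes". Sleep maintenance: "sWASO at Study Baseline is ≥ 60 minutes and mean sWASO at 6 months is ≤ 60 minutes", plus a reduction of more than 10 minutes.
- SAP 2 repeats both: "sSOL at Study Baseline was ≥ 30 minutes and mean sSOL at 6 months was ≤ 20 minutes" and "sWASO at Study Baseline was ≥ 60 minutes and mean sWASO at 6 months was ≤ 60 minutes".
- The protocol has the same cuts in the Synopsis (secondary endpoints and sample size rationale), 9.7.1.1.2 and 9.7.2.

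Strict cuts, all in SAP 3.4.2.4:

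- Period 1 definitions: "The sleep onset responder is defined as: sSOL at Study Baseline is >30 minutes and mean sSOL at each month" and "The sleep maintenance responder is defined as: sWASO at Study Baseline is >60 minutes".
- Analysed population: "The proportion of responders will be analyzed based on the subjects with sSOL > 30 minutes at the baseline for sSOL", with a parallel clause at >60 for sWASO.
- The Months 7–12 definitions and their population sentence use the same strict signs, for both Study Baseline and Period 2 Baseline.

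SAP 5 lists the major changes to the planned methods and does not mention a responder threshold. It refers to Table 1 for the full list. The Table 1 entry on other secondary efficacy measures records only that responders were clarified; it names no cut.

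**The concern.** One secondary endpoint has two definitions inside the same SAP, and one of them departs from the protocol. Responder proportions are a named secondary objective and are tested against placebo with a CMH test through Month 6. A programmer working from 3.1.2 would code ≥; one working from 3.4.2.4 would code >. The choice decides whether subjects exactly at 30 or 60 minutes can count as responders and, under 3.4.2.4, whether they are in the analysis at all.

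The population sentences raise a second ambiguity. The protocol, SAP 2 and SAP 3.1.2 put the baseline cut inside the definition of a responder and say nothing about limiting who is analysed. Only 3.4.2.4 limits the denominator. If both matters stay open when the sponsor is unblinded after Period 1, the operator and the denominator could be chosen with results in view.

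**Working it through.** **What each rule does.** Take an arm of N subjects, E with a baseline mean above the cut and T exactly at it, with responders R_E and R_T.

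- Inclusive cut, restricted denominator: (R_E + R_T)/(E + T)
- Strict cut, restricted denominator (SAP 3.4.2.4): R_E/E
- Inclusive cut, all subjects (a natural reading of the protocol and SAP 2): (R_E + R_T)/N
- Strict cut, all subjects: R_E/N

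The operator changes numerator and denominator together only where the denominator is restricted. With all subjects as denominator it changes the numerator alone.

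**Inputs.** 900 subjects at 1:1:1, so 300 per arm; two-sided alpha 0.05; differences of 16 points (onset) and 24.4 points (maintenance); stated power >99% (SAP 2, protocol 9.7.2). The baseline is the mean of the last 7 run-in diary mornings (SAP 6.1.1). The documents give neither a placebo responder rate nor the number at the cut, so both are varied as assumptions.

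**Reproducing the stated power.** For placebo rate p and difference d, with p̄ = p + d/2:

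z = [d − 1.96·√(2p̄(1−p̄)/n)] / √[(p(1−p) + (p+d)(1−p−d))/n], and power = Φ(z).

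- d = 0.16, p = 0.20, n = 300: z = (0.16 − 0.0719)/0.0361 = 2.44, power 99.27%.
- d = 0.16, p = 0.42 (the worst case): z = (0.16 − 0.0800)/0.0403 = 1.98, power 97.64%.
- d = 0.244: above 99.99% at every placebo rate.

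So >99% holds for 24.4 points throughout. For 16 points it holds when the placebo rate is about 22.5% or less, or about 61.5% or more; elsewhere it falls short by at most 99 − 97.64 = 1.36 points.

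**Effect of the operator.** Suppose a share t of each 300-subject arm sits exactly at the cut and is dropped, so n = 300(1 − t):

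| t | n per arm | Power, 16 points, p = 20% | Power, 16 points, p = 42% |
|---|---|---|---|
| 0 | 300 | 99.27% | 97.64% |
| 1% | 297 | 99.23% | 97.53% |
| 3% | 291 | 99.13% | 97.29% |
| 5% | 285 | 99.01% | 97.02% |
| 10% | 270 | 98.67% | 96.25% |

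For t of 1–5% the largest loss is 97.64 − 97.02 = 0.62 points. Power for 24.4 points stays at 99.99% or more.

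**Effect on the reported rate.** Let subjects above the cut respond at 20% and those at the cut at rate r between 0% and 50%. The inclusive rate is (1 − t)·20% + t·r: 19.8–20.3% at t = 1%, 19.0–21.5% at t = 5% and 18.0–23.0% at t = 10%, against 20.0% under the strict cut.

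**Effect of the denominator.** Entry needs onset and/or maintenance symptoms, so part of each arm may fall below one of the cuts. If 70% or 50% of an arm qualified (assumed), n would be 210 or 150, and power for 16 points at p = 20% would be 95.72% or 87.38%. Dropping a further 5% as ties would give 94.79% or 85.66%. Under these assumptions the restriction matters more than the ties.

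**The case against.** The case against making much of this is strong on size. The cut applies to a 7-night mean, so exact ties are rarer than on single nights. Any count of them needs distributions and rounding habits that the documents do not supply. The baseline is fixed before randomization and the rule is the same in every arm. The endpoint lies outside the gate-keeping sequence (SAP 3.3.3) and carries no multiplicity adjustment. All of that stands, and it limits the point to a correction of definition.

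Three further points also stand. The entry criteria use ≥30 and ≥60, but they count individual nights, so they do not settle which operator belongs on a weekly mean. Derivation specifications and table shells are separate documents (SAP 7 and 9), so it cannot be said which operator was programmed. And the protocol has neither a restricted denominator nor a Period 2 Baseline version, so agreement with the protocol can be claimed only for the Study Baseline definition.

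What does not stand is that the difference is a printing fault or an authorised change. The ≤ signs survive in the same sentences of 3.4.2.4, the strict sign recurs in every definition and population sentence there, and neither SAP 5 nor Table 1 names a new threshold.

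**Conclusion.** SAP 3.4.2.4 contradicts the protocol endpoint and SAP 2 and 3.1.2 on the baseline cut, without a declared change. The contradiction follows from the text alone.

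Its numerical effect is probably small. The loss of at most about 0.6 points of power rests on an assumed 1–5% of subjects at the cut, 300 analysable subjects per arm and the least favourable placebo rate. From a smaller qualifying set the same 5% costs more: at p = 42%, 90.93% to 89.47% with 210 per arm, and 79.44% to 77.36% with 150.

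A reader might infer that the strict cut biases the treatment comparison, or that it threatens a primary or key secondary conclusion. The documents support neither: the cut is pre-randomization and common to all arms, and no gate-kept test uses it. Nor do they support any particular number of affected subjects.

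**What to change.** Before Period 1 unblinding:

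1. In SAP 3.4.2.4, use ≥30 (sSOL) and ≥60 (sWASO) in the Study Baseline responder definitions, to match the protocol endpoint.
2. Apply the same operator to the Period 2 Baseline version and to the analysed-population sentences. The reason here is internal consistency, since the protocol has no counterpart.
3. State the denominator explicitly: all FAS subjects, or only those at or above the cut. If it is restricted, say so in SAP 3.1.2 and note in SAP 2 that the responder power statement is based on 900 subjects.
4. If the strict cut is intended, declare it in SAP 5 with a reason and align SAP 2 and 3.1.2.

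The cost is a few lines of SAP text, a check of the derivation specification and, if that specification uses the strict sign, a change of comparison operator. No new data are needed.
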